## 2.4.4 Analyses of efficacy endpoints

### 2.4.4.1 Analysis of primary efficacy endpoint(s)

#### 2.4.4.1.1 Primary efficacy analysis

The percent change from baseline in calculated LDL-C at Week 24 as defined in [Section 2.1.3.1](#) will be analyzed in the ITT population using a mixed effect model with repeated measures (MMRM) approach. All post-baseline data available within Week 4 and Week 24 analysis windows will be used and missing data are accounted for by the MMRM model. The model will include the fixed categorical effects of treatment group (ezetimibe versus alirocumab), randomization strata (as per IVRS, as defined in [Section 1.1](#)), time point (Week 4, Week 8, Week 12, Week 16, and Week 24 as defined in [Section 2.5.4](#)), treatment -by-time point interaction, strata-by-time point interaction, and the continuous fixed covariates of baseline LDL-C value and baseline value-by-time point interaction. In case the number of patients is lower than 10 in a given stratum (eg, MI/Ischemic Stroke = Yes), the corresponding stratum (eg, MI/Ischemic stroke) and stratum-by-time point interaction terms will be removed from the model. The same will be applied to sensitivity analyses and subgroup analyses.

This model will be run using SAS Mixed procedure with an unstructured correlation matrix to model the within-patient errors. Parameters will be estimated using restricted maximum likelihood method with the Newton-Raphson algorithm. Denominator degrees of freedom will be estimated using Satterthwaite's approximation. This model will provide baseline adjusted LS means estimates at Week 24 for both treatment groups with their corresponding standard errors (SEs) and 95% confidence intervals (CIs). To compare the alirocumab group to the ezetimibe group, an appropriate contrast statement will be used to test the differences of these estimates, at the 2-sided 0.05 level.

Within group least square (LS) means and SEs will be provided, using weights equal to the observed proportion of patients in strata variable levels in the study population (ie, "population weight") rather than equal weights. Population weights are considered more appropriate than equal coefficients due to unbalances between levels of the randomization stratification factors observed in the study population.

Let  $\mu_0$  and  $\mu_1$  be the population means of the percent change from baseline in calculated LDL-C at Week 24 under ezetimibe and alirocumab, respectively. The hypothesis that will be tested is " $H_0: \mu_0 = \mu_1$ " versus " $H_1: \mu_0 \neq \mu_1$ ".

The MMRM model relies on the "missing-at-random" (MAR) assumption. As we can never exclude the possibility for a not-missing-at-random (NMAR) missingness mechanism, sensitivity analyses to explore the impact of non-ignorable missingness on the primary efficacy analysis will be conducted (see pattern mixture model defined in [Section 2.4.4.1.4](#)).

#### 2.4.4.1.2 Model assumption checks

##### ***Homogeneity of treatment effect across baseline LDL-C levels***

In order to check the homogeneity of treatment effect versus baseline LDL-C, the following interaction terms will be added in the primary MMRM model:

- Treatment group \* baseline calculated LDL-C
- Treatment group \* time-point \* baseline calculated LDL-C

Within the framework of this model with interaction terms, a graph presenting the LS means difference versus ezetimibe at Week 24 and the corresponding 95% CI will be provided by baseline LDL-C value.

##### ***Analysis of residuals:***

The analysis of the residuals of the MMRM will be primarily based on studentized residuals. It will include:

- Normality of studentized residuals, presented graphically using histogram and quantile quantile (QQ)-plot;
- Plot of studentized residuals versus predicted values;
- Distribution of studentized residuals, presented graphically using boxplots, within each category of the fixed categorical effects of the MMRM:
  - Treatment group (ezetimibe, alirocumab);
  - Time point (Week 4, Week 8, Week 12, Week 16, Week 24);
  - Treatment-by-time point interaction;
  - Randomization strata;
  - Randomization strata-by time point interaction.

#### 2.4.4.1.3 Sensitivity to randomization strata

In order to assess the robustness of the primary analysis to randomization stratum mistakes (ie, the stratum recorded in IVRS differs from the actual one), the MMRM model will be re-run including the actual stratum as per the e-CRF instead of the stratum recorded in IVRS.

#### 2.4.4.1.4 Sensitivity to handling of missing data

Sensitivity analyses will be conducted to assess the robustness of primary efficacy analysis with regards to handling of missing data (1).

##### **Visual examination:**

- In order to explore the missing data pattern, post-baseline calculated LDL-C observations (in the ITT population) will be described according to the following groups:
  - Calculated LDL-C available at Week 24\*(ie, primary efficacy endpoint available);
  - Calculated LDL-C available at Week 16\* but missing at Week 24 \*;

- Calculated LDL-C available at Week 12\* but missing from Week 16\*;
- Calculated LDL-C available at Week 8\* but missing from Week 12\*;
- Calculated LDL-C available at Week 4\* but missing from Week 8\*;
- Calculated LDL-C missing from Week 4\*.

(\*): as defined in [Section 2.5.4](#)

Then, a graph of mean LDL-C calculated levels (respectively percent change from baseline in calculated LDL-C)  $\pm$  SE at baseline, Week 4, Week 8, Week 12, Week 16, and Week 24 will be provided by missing data pattern, for each treatment group.

- In the ITT population, demographic and baseline characteristics will be described within the missing data pattern number 1 versus the pooled others. P-values from Fisher exact test for categorical data and from asymptotic 1-way ANOVA test for Wilcoxon scores (Kruskal-Wallis test) for continuous data will be also provided for descriptive purposes.

#### Multiple imputations (under MAR assumption)

In addition to the MMRM method, the multiple imputation (MI) method will be used to address missing values, in the randomized population, followed by the testing of treatment arms using an analysis of covariance (ANCOVA) model, with the intent to evaluate the robustness of the primary analysis using a different statistical method. The imputation model described in [Section 2.4.4.2.2](#) will be used but without log transformation. Missing data from the randomized population will be imputed 100 times to generate 100 complete data sets. The percent change from baseline at Week 24 will be then derived from observed and imputed LDL-C at this time point. The 100 complete data sets will be then analyzed using an ANCOVA model with treatment group and randomization strata (as per IVRS, as defined in [Section 1.1](#)) as fixed effects, and the baseline calculated LDL-C value as continuous covariate, and the MIANALYZE procedure will be used to generate valid statistical inferences by combining results from the 100 analyses using Rubin's formulae [\(1\)](#).

- The number of imputations (100) will be informally verified by replicating sets of 100 imputations and checking whether the combined results are stable. If not stable, the number of imputations will be increased and informally checked as above, and thus until stable estimates are obtained.

In addition, for each simulation leading to negative imputed value, another value will be redrawn using MINIMUM option of MI SAS procedure [\(2\)](#).

#### Pattern mixture model (see [Appendix B](#) for more details)

Multiple imputations will be used with different imputation strategies applied to calculated LDL-C values missing during the on-treatment period (i.e. within the time period from the first double-blind IMP injection up to the day of last injection + 21 days) versus calculated LDL-C values missing after treatment discontinuation (ie, after the day of last injection + 21 days) based on the following assumptions:

- Patients within 21 days of their last blind IMP injection would continue to show benefit from treatment similar to that observed at the scheduled time point. Therefore, calculated LDL-C values missing during the on-treatment period (eg, samples obtained out-side the

specified window, no blood sample available although visit was performed) should be considered “missing-at-random” and imputed based on other on-treatment measurements.

- Patients who stopped taking their study treatment no longer benefited from it after discontinuation, and thus tended to have calculated LDL-C values returning to baseline. Therefore, calculated LDL-C values missing more than 21 days after treatment discontinuation should be imputed based on patient’s own baseline value.

Missing calculated LDL-C values will be imputed 100 times to generate 100 complete data sets. The percent change from baseline to Week 24 will be derived from observed and imputed LDL-C at this time point. The completed data sets will be analyzed using an ANCOVA model with treatment group and randomization strata as fixed effects, and the baseline calculated LDL-C value as continuous covariate. The results from the 100 analyses will be combined using Rubin’s formulae.

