8.1.2 Timing of administration

A training injection is planned on Week -1 (V2) with a placebo for alirocumab. A second training injection with placebo for alirocumab may be administered between Week -1 and randomization visit.

During the double-blind treatment period, alirocumab or placebo for alirocumab will be administered SC Q2W, starting at Week 0 continuing up to the last injection (Week 22) 2 weeks before the end of the DBTP. If the injection is scheduled to take place on the same date as the site visit, then the IMP should be administered after the blood sampling has been completed.

Further training with the scheduled double-blind alirocumab IMP can be done between W 0 and W 4 and at additional scheduled or unscheduled visits, as per investigator's judgment.

Double-blind IMP will start as soon as possible after the call for randomization using the treatment kit number provided by the IVRS/IWRS. The first injection after randomization will be done at the site by the patient or another designated person (such as spouse, relative, etc) under direct site staff supervision. Patients will be monitored at the investigational site for at least 30 minutes after this first double-blind injection.

Alirocumab IMP injection should be administered Q2W SC at approximately the same time of the day; however it is acceptable to have a window period of ± 3 days. The time of the day is based on patient's preference.

If by mistake or due to other circumstances an injection is delayed by more than 7 days or completely missed, then the patient should return to the original schedule of study treatment administration without administering delayed injections. On the other hand, if the delay is less than or equal to 7 days from the missed date, then the patient should administer the delayed injection and then resume the original schedule of study treatment administration.

Ezetimibe 10 mg or placebo for ezetimibe capsules will be taken orally once daily at approximately the same time of the day, with or without food. Preferably, on the injection days the IMP capsule will be administered roughly at the time of injection (either before or shortly after). The capsules must be taken until the day before the end-of-treatment visit (early or not), and not stopped at the time of the last injection.

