### ***Observation period***

The period of safety observation starts from the time when the patient gives informed consent and is divided into the following periods:

- The PRE-TREATMENT period: defined as the time from the signed informed consent up to the first dose of double-blind IMP;
- The treatment-emergent adverse event (TEAE) period: defined as the time from the first dose of double-blind IMP up to the day of last dose of double-blind IMP injection+70 days (10 weeks) as residual effect of alirocumab is possible until 10 weeks after the discontinuation of double-blind IMP injection.

The TEAE period will include:

- The TREATMENT period defined as the time from the first dose of double-blind IMP up to the day of last dose of double-blind IMP injection + 21 days, as serum concentration of alirocumab is expected to be  $>10 \mu\text{g/mL}$  for approximately 21 days following administration of 150 mg, and because throughout the previous studies it was observed that when alirocumab concentrations declined below this concentration, decrease in effect on LDL-C is observed.
- The RESIDUAL TREATMENT defined as the time from the day of last dose of double-blind IMP injection + 22 days up to the day of last dose of double-blind IMP injection + 70 days (10 weeks).
- The POST-TREATMENT period: defined as the time starting the day after the end of the TEAE period (ie, 71 days after the day of last dose of double-blind IMP injection).

The on-study observation period is defined as the time from the day of first dose of double-blind IMP (capsule or injection, whichever comes first) until the last protocol planned visit of the patient. The last protocol planned visit is defined as the follow-up visit if done, or else 32 weeks after the randomization of the patient.

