#### ***2.4.3.1 Extent of investigational medicinal product exposure***

##### ***Injection (alirocumab or placebo)***

The extent of IMP exposure will be assessed by the duration of IMP exposure, and actual dose information.

Double-blinded IMP injections are those administered from randomization to completion or discontinuation of the study treatment. These injections contain:

- Placebo for patients randomized in the ezetimibe group;
- 75 or 150mg of alirocumab for patients randomized in the alirocumab group.

Total exposure will be assessed using descriptive statistics for:

- Duration of IMP injection exposure in weeks is defined as: (last dose of double-blind IMP injection date – first dose of double-blind IMP injection date + 14 days)/7, regardless of unplanned intermittent discontinuations (see [Section 2.5.3](#) for calculation in case of missing or incomplete data). Non-integer values will be rounded to 1 decimal place;
- The total number of injections by patient.

These parameters will be also analyzed per dose of alirocumab using similar definitions.

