### ***Date of last dose of IMP***

The date of last injection is equal to the last date of administration reported on injection administration case report form page, or missing if the last administration date is unknown.

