## Appendix B Detailed statistical methodology for pattern mixture model

As a sensitivity analysis of the primary efficacy endpoint (i.e. percent change from baseline to Week 24 in calculated LDL-C), a pattern-mixture model approach will be used, with a different imputation strategy applied for missing calculated LDL-C values during the on-treatment period (ie, within the time period from the first double-blind IMP injection up to the day of the last injection +21 days) and missing calculated LDL-C values after treatment discontinuation (ie, after the day of last injection +21 days) based on the following assumptions:

- Patients within 21 days of their last IMP injection would continue to show benefit from treatment similar to that observed at the scheduled time point. Therefore, calculated LDL-C values missing during the on-treatment period will be considered “Missing At Random” and imputed using a model estimated using all samples collected on treatment.
- Patients who stopped taking their study treatment no longer benefited from it in the future, and thus tended to have calculated LDL-C values returning to baseline. Thus calculated LDL-C values missing after treatment discontinuation will be imputed based on patient’s own baseline value.

The assumptions for this approach are based on the following considerations:

- Missing values during the on-treatment period are mostly consecutive to:
  - Visits performed outside of the pre-specified time-window
  - No blood sample available although visit was done
  - Calculated LDL-C not measurable due to technical reasons

In addition, these missing data are often intermittent, i.e. followed by calculated LDL-C values collected at subsequent visits. It is therefore considered reasonable to assume that these missing data were “At Random”.

- Phase 2 studies DFI11565 and R727-CL-1003 included a prospective assessment of calculated LDL-C during the follow-up period after a 12-week treatment period. These studies showed that after treatment discontinuation, the average calculated LDL-C returned to baseline level within 4 weeks after ceasing alirocumab treatment.

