### Imputation of missing data during the on-treatment period

Missing calculated LDL-C values during the on-treatment period will be imputed from other on-treatment measurements assuming Missing At Random, using SAS MI procedure.

Only calculated LDL-C values collected during the on-treatment period will be included in the imputation model. This way, missing calculated LDL-C values during the on-treatment period will be imputed based solely on observed on-treatment calculated LDL-C values.

The imputation model will include the treatment arm, baseline calculated LDL-C value and all calculated LDL-C values at pre-specified visits. Since the pattern of missing data is necessarily non-monotone, a Monte-Carlo Markov Chain (MCMC) method is used. A minimum value of 0 will be specified in order to avoid negative imputed LDL-C values.

A sample SAS code is provided below:

```
proc mi data=DATAIN out=DATAOUT nimpute=100 minimum=0;  
var ARM LDL_BASE LDL_W4 LDL_W8 LDL_W12 LDL_W16 LDL_W24;  
run;
```

As stated above, the input dataset DATAIN will include only calculated LDL-C values collected during the on-treatment period. Any calculated LDL-C values collected during the post-treatment period will be excluded from the input dataset. In practice, the MI procedure generates imputed values for all missing values (whether on-treatment or post-treatment), but only imputed values during the on-treatment period will be kept in the final datasets that will be analyzed using ANCOVA. Imputed values during the post-treatment period will be discarded and replaced by imputed values described in the next paragraph.

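### The pattern mixture model dates treatment in the ezetimibe arm by a placebo injection, so a missing Week 24 LDL-C there can be imputed the wrong way

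*SAP*

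**What the plan says.** SAP 2.4.4.1.1 sends the question of non-ignorable missingness to the pattern mixture model. SAP 2.4.4.1.4 then defines the on-treatment period as "within the time period from the first double-blind IMP injection up to the day of last injection + 21 days", and Appendix B repeats it: "within the time period from the first double-blind IMP injection up to the day of the last injection +21 days". Neither place separates the arms or uses a capsule date. A missing calculated LDL-C inside the period is imputed as missing at random from on-treatment data. One after it is drawn from a normal distribution centred on the patient's own baseline.

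The same period selects the input data: "Only calculated LDL-C values collected during the on-treatment period will be included in the imputation model".

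On what the injection is, SAP 2.4.3.1 lists "Placebo for patients randomized in the ezetimibe group". On its date, SAP 2.5.1 says: "The date of last injection is equal to the last date of administration reported on injection administration case report form page".

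Both supporting arguments concern alirocumab. SAP 2.1.4 bases the 21 days on serum concentrations, noting that "when alirocumab concentrations declined below this concentration, decrease in effect on LDL-C is observed". Appendix B bases the return to baseline on phase 2 studies in which "the average calculated LDL-C returned to baseline level within 4 weeks after ceasing alirocumab treatment".

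Elsewhere the SAP does use capsules. The efficacy treatment period in 2.3.1.2 ends at the earlier of last injection + 21 days and last capsule + 3 days, and 2.5.3 says what to do when the last capsule date is missing.

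**The concern.** The model states a clear assumption: patients on treatment keep the benefit, and patients who stop return to baseline. In the ezetimibe arm it applies that assumption by the date of a placebo injection. Patients who take both components to the end are classified correctly, and so are those who stop both by day 154. The rule fails in three situations:

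- (a) Placebo injections stop and ezetimibe continues. The missing value is drawn around baseline although the patient is on active drug. This makes ezetimibe look worse and inflates the alirocumab advantage.
- (b) Ezetimibe stops and placebo injections continue. The missing value is imputed as still benefiting. This understates the advantage.
- (c) Both stop together late in treatment. The 21-day alirocumab carry-over is credited to ezetimibe. This is also conservative.

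Situation (a) does not require anyone to discontinue. Protocol 8.1.2 says that if "an injection is delayed by more than 7 days or completely missed, then the patient should return to the original schedule", with no make-up dose, while capsules run to the day before the end-of-treatment visit. Protocol 10.3.1 also foresees interruption of injections or of capsules. The patient need not miss the Week 24 visit either. When triglycerides exceed 400 mg/dL the laboratory measures LDL-C instead of calculating it (Protocol 9.1.3.1), and SAP 2.1.3 bars measured values from the calculated LDL-C endpoints.

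At stake is the credibility of the one modelled departure from missing at random. It should not carry an error that can favour the test drug.

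**Working it through.** **Inputs.** Difference 20 points, SD 25, two-sided 0.05 (Protocol 11.1, SAP 1.3). Arms of 400 and 200 (Protocol 11.1). Expected ezetimibe effect 25-30% (Protocol section 4, rationale for the design). Injections every 2 weeks, last at Week 22 (Protocol 8.1.2). Week 24 target day 169 (SAP Table 2). The documents give no rate of missing Week 24 values or of discordant capsule and injection status, so all shares below are assumptions.

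**Planning figure.** A two-sample t-test with 64 and 32 patients has power 95.5%; with 62 and 31 it has 94.9%. The stated 96 is reproduced as the smallest 2:1 design reaching 95%.

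**Which patients are misdated.** Injections fall on days 1, 15, ..., 141, 155. The SAP does not date a missing value, so I place it at day 169.

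- Last injection on day 155: 155 + 21 = 176, on treatment at day 169.
- Last injection on day 141 (only Week 22 missed): 141 + 21 = 162, off treatment 7 days before day 169, even if capsules continue.

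Both results hold over the ±3-day visit window (days 166-172) combined with the ±3-day injection window: 138-144 + 21 = 159-165, and 152-158 + 21 = 173-179. One exception is a Week 20 injection given 7 days late, as Protocol 8.1.2 permits, followed by a missed Week 22 injection: 148 + 21 = 169, on treatment at the target day.

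**Joint stops (c).** If both components stop on day s, the injection rule gives on treatment at day 169 only for s of 155 or later. For s of 148-154 the last injection was day 141, so both rules say off. A capsule rule with lag L gives on treatment for s of 169 - L or later.

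| Capsule lag | Days on which the rules disagree |
|---|---|
| 3 days | 155-165 (11 days) |
| 7 days | 155-161 (7 days) |
| 14 days | none |

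Assume 5-20% of the arm stop jointly with a missing Week 24 value, uniformly over 168 days. With the 3-day lag this affects 200 × 0.05 × 11/168 = 0.65 to 200 × 0.20 × 11/168 = 2.6 patients. The shift is 0.65/200 × 25 = 0.08 to 2.6/200 × 30 = 0.39 points.

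**Size in general.** Shift in the ezetimibe mean = share of the arm wrongly imputed × 25 to 30. The share counts only patients who are both misclassified and missing a calculated Week 24 value; an observed value is kept.

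| Share of arm | Patients | Shift (points) | Simulated shift |
|---|---|---|---|
| 1% | 2 | 0.25-0.30 | 0.25-0.31 |
| 2% | 4 | 0.5-0.6 | 0.49-0.59 |
| 5% | 10 | 1.25-1.5 | 1.25-1.51 |
| 10% | 20 | 2.5-3.0 | 2.51-2.99 |

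The last column simulates the Appendix B baseline draw against an on-treatment draw, assuming a baseline mean of 110 and SD of 30 mg/dL. Since (a) opposes (b) and (c), the net shift is (share in a - share in b and c) × 25 to 30.

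**Against the precision of the trial.** SE = 25 × √(1/400 + 1/200) = 2.165, and the smallest significant difference is 1.96 × 2.165 = 4.24. Taking a 20-point estimate down to that needs (20 - 4.24)/30 = 52.5% to (20 - 4.24)/25 = 63.0% of the ezetimibe arm misclassified in one direction.

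**Input data.** The dataset for the on-treatment imputation is cut by the same injection date. Values taken off ezetimibe but within 21 days of a placebo injection enter it, and values on ezetimibe after that date are excluded. The documents do not allow this part to be sized.

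**The case against.** The strongest case is that this hardly matters. A patient must have discordant components and also no calculated LDL-C anywhere in the Week 24 window (days 155-182). Protocol 10.3.4 keeps patients who stop treatment in the visit schedule and asks for every effort to obtain Week 24. Nothing in the documents suggests 5% or 10% of the arm would qualify, the errors partly cancel, and the primary MMRM is untouched. That stands as a limit on size. It does not make the rule correct, and the net direction cannot be known in advance.

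Second, the model is not the only look at missing data. SAP 2.4.4.1.4 also plans LDL-C profiles by missing-data pattern and a baseline comparison of patients with and without Week 24 data. Those are descriptive; the other imputation analysis assumes missing at random.

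Third, placing a missing value at day 169 is an assumption, and a Week 20 injection given 7 days late escapes the example. Both are true, and the exception is narrow.

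Fourth, a capsule-based rule brings its own asymmetry: 21 days of carry-over for alirocumab against 3 for ezetimibe, with no ezetimibe washout data in the documents. With the 3-day lag, patients stopping both on days 155-165 would be imputed as benefiting in one arm and at baseline in the other, which moves the estimate towards alirocumab. This is fair, and it is why the lag should be labelled an assumption and varied. With 14 days the joint-stop classification is the same as now, while (a) and, for longer gaps, (b) are still corrected.

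**Conclusion.** The concern holds. The rule as written contradicts the model's own assumption for ezetimibe patients whose capsule and injection status differ and whose Week 24 value is missing. It also filters the imputation model's input data by the wrong date. The bias is 0.25-0.30 points for each 1% of the ezetimibe arm misclassified in one direction, so 1.25-1.5 points at 5%, or about 0.6-0.7 of a standard error. Situation (a) favours alirocumab; (b) and (c) work against it. These figures rest on the protocol's expected ezetimibe effect, 200 ezetimibe patients, a missing value dated to day 169, and assumed shares. The superiority conclusion is not threatened at the planned difference. The definition should be corrected because it affects the only modelled check outside missing at random and the correction is simple.

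**What to change.** In SAP 2.4.4.1.4 and Appendix B, define the on-treatment period by each arm's active component. Suggested text:

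> Alirocumab arm: first injection to last injection + 21 days. Ezetimibe arm: first capsule to last capsule + 3 days. The 3-day lag is an assumption; the analysis will be repeated with 14 days. A missing value is dated to its targeted study day in Table 2. The same rule selects the observed values in DATAIN.

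Report by arm how many patients have discordant capsule and injection status and a missing Week 24 value.

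Do not substitute the efficacy treatment period of 2.3.1.2. Because it ends at whichever component stops first, it leaves error (a) in place and would class alirocumab patients who stop only the placebo capsule as off treatment.

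The cost is a few sentences in two SAP sections, one derived date per ezetimibe patient and one repeat run. Capsule dates are already collected, and the missing-date rule in 2.5.3 can be reused. No new data are needed.
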